### **Sub-populations:**

Data will be stratified by prophylaxis dosing regimen (following approved local label, see Section 9.7.3), severity of hemophilia (mild, moderate, or severe), severity of patient bleeding profile at baseline (ABR in the last 12 months prior to enrollment), medical history (in particular joint status [affected joint: yes/no; 1 affected joint/>1 affected joint]), age groups, and time on treatment (i.e., damoctocog alfa pegol-naive or not). The prophylaxis-dosing regimen as prescribed by the physician at the beginning of the study will be used for stratification, unless otherwise stated.

Assignment of patients into treatment categories in case of changes to the regimen or switch to on-demand will be specified within SAP. Whenever reasonable, further subgroups (e.g., sex, baseline patient/disease/pre-treatment characteristics) will be specified in the SAP. Selected tables (including safety events, treatment administration and prophylaxis regimen) will be presented by history of inhibitors and exposure days (to FVIII product) at baseline.

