## 9. Research methods

### 9.1 Study design

This is a multinational, open-label, prospective, non-interventional, multicenter, cohort study of PTPs with hemophilia A receiving damoctocog alfa pegol with any kind of treatment modality (on-demand, prophylaxis, or intermittent prophylaxis). The study is planned to be conducted in multiple countries depending on timing of regulatory approval and national reimbursement access.

Prospective data will include prophylaxis regimen effectiveness measured by the number of ABR (reported in patient infusion diaries or documented by physicians, if patient infusion diary is not available), drug usage (IU/kg/infusion, IU/kg/year, and IU/kg/event), regimens used, patient-reported outcome (PRO) measurements (where applicable), such as validated, disease-specific and generic quality of life questionnaires and treatment satisfaction; as well as PK parameters (when available), joint outcomes (HJHS), and safety including AEs of special interest (hypersensitivity reactions, loss of drug effect, renal impairment, neurocognitive disorders, and inhibitor development) and drug-related ARs in standard clinical practice. Retrospective data will include documentation of previous therapy, lifetime duration on prophylaxis, medical condition, PK parameters (when available), and bleeds up to 12 months prior to use of damoctocog alfa pegol, in order to allow a stratification of patients by patient bleeding profile and disease characteristics (See Section 9.3.7).

Patients/legal representatives and physicians can choose from different prophylaxis regimens with damoctocog alfa pegol following approved local labels or any other regimen prescribed by the physician as part of normal clinical practice. Patients/legal representatives and physicians can choose to change the dosing regimen based on the patient's response to treatment at any time. A reason for the dose and/or frequency change should be documented.

The patients planned observation period will be 36 months (with the potential for further extension), for the collection of long-term safety data and continuous prospective monitoring of joint health status over time.

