### **9.1.2 Secondary endpoints**

The secondary endpoints are:

- Occurrence, duration, treatment, severity, and outcome of AEs of special interest (hypersensitivity reactions, loss of drug effect, renal impairment, neurocognitive disorders, and inhibitor development), AEs, SAEs, and ARs.
- Hemostasis during surgery measured by number of infusions and consumption of FVIII product
- Change in joint scores (HJHS) from baseline to 12 months, to 24 months, to 36 months.
- Joint status evaluation by ultrasound (HEAD-US score), if available or part of standard clinical practice.
- Number of affected joints by patient, and the change from baseline to 12 months, to 24 months and to 36 months.
- Annualized number of spontaneous, joint, and trauma bleeds.
- Number of reported bleeds (total, spontaneous, joint, and trauma) during the study compared with number of reported bleeds (total, spontaneous, joint, and trauma) for previous FVIII products in the 12 months prior to enrollment into the study.
- Proportion of patients with 0 bleeds, and the difference in proportion comparing to previous prophylaxis treatment.
- Description of PK parameters for previous FVIII products versus damoctocog alfa pegol (if available in routine clinical practice).
- Efficacy of treatment of break-through bleeds.
- Change from baseline to 12 months, to 24 months and to 36 months in treatment satisfaction (Hemo-SAT A score).
- Change from baseline to 12 months, to 24 months and to 36 months in treatment satisfaction (Hemo-QoL [A and SF] score).

- Change from baseline to 12 months, to 24 months and to 36 months in work productivity and activity impairment (WPAI score).

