### 9.2.2 Eligibility criteria

#### 9.2.2.1 Inclusion criteria

- Diagnosis of hemophilia A.
- Patients previously treated for Hemophilia A.
- Patients without previous history of inhibitors or patients with previous history of inhibitors on standard prophylaxis therapy for at least 1 year prior to study entry.
- No current evidence\* of FVIII inhibitor or clinical suspicion\*\* of FVIII inhibitor.
  - \* Evidence of FVIII inhibitor as measured by the Nijmegen-modified Bethesda assay [ $<0.6$  Bethesda units (BU/mL)] or Bethesda assay [ $<1.0$  BU/mL] in 2 on consecutive samples.
  - \*\* Documented or clinical suspicion of shortened FVIII half-life ( $<6$  hours).
- Initiation of or currently on damoctocog alfa pegol with any kind of treatment modality (on-demand, prophylaxis, or intermittent prophylaxis).
- Signed informed consent/assent.

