### 9.3.2 Variables to determine the secondary endpoints

The variables for secondary endpoints are:

- Safety:
  - Occurrence, duration, treatment, severity, and outcome of AEs, SAEs, and ARs (including AEs of special interest [hypersensitivity reactions, loss of drug effect, renal impairment, neurocognitive disorders, and inhibitor development]).
- Effectiveness:
  - Number of reported total, spontaneous, joint, and trauma bleeds.
  - Retrospective (diagnosed clinically, by imaging, by the patient, or by the physician) and prospective location and number of affected joints.
  - Joint health measured by HJHS.
  - Newly affected joints (number and location).
  - Reported bleeds (number, type, location) during study and up to 12 months prior to start of therapy with damoctocog alfa pegol. Prior bleeds to be estimated by the patient and the physician. Reported bleeds during the study will be recorded in the patient infusion diary and serious, life-threatening bleeds and surgery bleeds will be documented by the physician.
  - Number of infusions and FVIII consumption to achieve hemostasis during surgery.
  - Patient-report outcome:
    - Treatment satisfaction measured by Hemo-SAT A.
    - Health-related quality of life measure by Hemo-QoL (A and SF).
    - Work productivity and activity impairment measured by WPAI [+ CIQ: HS].

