### 9.3.4 Hemophilia Disease history

Disease history describes any medical findings that are relevant to the underlying disease and were present before enrollment into the study. Findings and diagnoses meeting the criteria listed below have to be documented, if available:

- Date of diagnosis (at least the year).
- Type of gene mutation, if available.
- Family history of hemophilia.
- Family history of inhibitors.
- Severity of hemophilia at initial diagnosis.
- Age/age group at first treatment with factor FVIII replacement therapy.
- Age at initiation of prophylaxis therapy, if applicable.
- Duration of prophylaxis treatment lifetime.
- Patient history of inhibitors (date, high/low titer, etc.).
- ITI history.
- Most recent FVIII product (name, treatment modality [on-demand, prophylaxis, or intermittent prophylaxis], dose/regimen) up to 12 months prior to start of therapy with damoctocog alfa pegol.
- PK parameters from most recent FVIII products, if available.
- Number and location of affected joints.
- Reported previous bleeds (number, type, and location) within 12 months prior to start of therapy with damoctocog alfa pegol.
- Ultrasound scanning (Hemophilia Early Arthropathy Detection with Ultrasound [HEAD-US]) to evaluate joints of patients with hemophilic arthropathy [28].

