### **9.7.2 Analysis of demography, disease details, prior and concomitant medication/treatment, and other baseline data**

Demographics and baseline disease characteristics will be described by frequency tables or summary statistics. Baseline disease characteristics will include the most recent FVIII product used prior to the start of damoctocog alfa pegol treatment. Some continuous variables will be categorized and presented in frequency tables in addition to summary statistics. Categories will be defined in the SAP.

Number of bleeds prior to enrollment (or first administration of the study drug, for damoctocog alfa pegol non-naïve patients) into the study will be summarized.

Prior and concomitant medication/treatment and medical history will be presented by frequency tables or summary statistics.

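### The bleeding-profile stratum and one before/after endpoint use the 12 months before enrollment, but prior bleeds are collected for the 12 months before damoctocog start; the two differ for patients already on the drug

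*Protocol*

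**What the plan says.** Two places in the protocol count the look-back from enrollment:

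- Section 9.7.1, Sub-populations, stratifies by "severity of patient bleeding profile at baseline (ABR in the last 12 months prior to enrollment".
- Section 9.1.2 compares bleeds during the study with those reported "for previous FVIII products in the 12 months prior to enrollment into the study".

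Neither makes an exception for patients who were already using the drug.

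The other places count it from damoctocog alfa pegol:

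- Section 9.1 collects "bleeds up to 12 months prior to use of damoctocog alfa pegol, in order to allow a stratification of patients by patient bleeding profile".
- Section 9.3.2 lists "Reported bleeds (number, type, location) during study and up to 12 months prior to start of therapy with damoctocog alfa pegol", and the Variables entry of the abstract agrees.
- Section 9.3.4 lists "Reported previous bleeds (number, type, and location) within 12 months prior to start of therapy with damoctocog alfa pegol".
- Section 9.7.2 summarizes bleeds before enrollment, with the alternative "or first administration of the study drug, for damoctocog alfa pegol non-naïve patients".
- Section 9.7.4 plans a comparison of ABR on damoctocog prophylaxis with the ABR before damoctocog treatment.

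The inclusion criteria in 9.2.2.1 admit patients on "Initiation of or currently on damoctocog alfa pegol with any kind of treatment modality". No upper limit on earlier use is stated.

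**The concern.** For a patient who starts the drug at enrollment the two anchors nearly coincide, and nothing goes wrong. For a patient already on it, they separate by the length of prior use. Enrollment is planned from Q2 2019 to Q2 2022 (abstract, Milestones), so prior use of a year or more is possible.

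Two things are at stake. First, the bleeding-profile stratum would not mean the same in every patient: how badly the patient bled before the drug in one group, and how the patient bled on the drug in the other. Section 9.3.1 lists bleeding profile among the variables for the primary endpoint, so ABR tables split by that stratum would inherit the mixture. Second, the endpoint in 9.1.2 asks for bleeding on previous FVIII products in a window that may hold little or no time on those products.

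**Working it through.** The protocol states no figure for this point, so there is none to reproduce. The check sets the sections side by side and then works out how far the windows diverge.

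**Step 1: what is collected against what is used.** Section 9.1 gives the purpose of the pre-drug bleed history as stratification by bleeding profile. Section 9.7.1 then defines that same stratum on another window. The bleed history listed in 9.3.2 and 9.3.4 stops at damoctocog start, and on-study bleeds begin at enrollment. For a non-naive patient the time between the two dates falls in the 9.7.1 window but in neither listed source.

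**Step 2: overlap of the enrollment window with the study drug.** Let m be the months of damoctocog use before enrollment, up to 12.

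- Share of the window on study drug = m/12.
- Months left for a previous FVIII product = 12 − m.

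| m (months) | share on drug | months left for previous product |
|---|---|---|
| 0 | 0% | 12 |
| 3 | 25% | 9 |
| 6 | 50% | 6 |
| 9 | 75% | 3 |
| 12 or more | 100% | 0 |

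The second column bears on the stratum in 9.7.1, the third on the comparator in 9.1.2.

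**Step 3: illustration for the stratum only.** Inputs: an on-drug ABR of 4, the prophylaxis value quoted in section 9.5 from the earlier trial, and a pre-drug ABR of 6 to 12, which is my assumption because the protocol gives none. It is also assumed that the on-drug bleeds before enrollment could somehow be obtained.

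ABR in the enrollment window = [(12 − m) × pre-drug ABR + m × on-drug ABR] / 12

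- m = 6, pre-drug 6: (6 × 6 + 6 × 4)/12 = 60/12 = 5.0
- m = 6, pre-drug 12: (6 × 12 + 6 × 4)/12 = 96/12 = 8.0
- m = 12, either pre-drug value: (12 × 4)/12 = 4.0

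So two patients whose pre-drug rates differ by a factor of two (6 and 12) would both show 4.0 after a year on the drug, and the stratum could not tell them apart. Anchored to drug start, they stay at 6 and 12 whatever the prior use.

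**Step 4: the comparator in 9.1.2.** That bullet restricts the comparator to previous FVIII products. The on-drug part of the window therefore drops out. What remains is 12 − m months, and nothing at 12 months or more.

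**The case against.** The strongest reply is that the intent can be recovered. Section 9.1 ties the pre-drug bleeds to the stratification, 9.7.2 makes the switch to first administration for non-naive patients, and 9.7.4 already compares with the pre-damoctocog ABR. Section 9.7.1 also stratifies by naive or non-naive status, section 9.7 leaves calculated variables to the SAP, and the study is descriptive with no hypothesis tests. All of this is fair and limits the weight of the point. It does not remove it: 9.1.2 and 9.7.1 do not leave the window open but state it, so a SAP that followed the other sections would contradict these two.

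Three stronger readings are tempting, and the documents do not support them.

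- A reader might infer that the before/after comparison sets the drug against itself and so drifts toward no change. The comparator in 9.1.2 is confined to previous FVIII products, and the on-drug bleeds before enrollment are not in the listed history. The result is a short or empty comparator, not a self-comparison. The ABR comparison in 9.7.4 has the right anchor already.
- A reader might infer that the regression adjusts away part of the drug's effect. No section names the enrollment-anchored ABR as a model covariate. Section 9.7.1 gives pre-treatment history as an example of a covariate, and 9.7.4 speaks only generally of treatment and disease characteristics.
- A reader might want a percentage for the dilution of a treatment effect. That would need a prior-product ABR, the non-naive share and each patient's time on drug. The protocol gives none of them.

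**Conclusion.** The protocol contradicts itself on the anchor of one look-back window, and the contradiction matters only for non-naive patients. Read literally, the stratum in 9.7.1 rests on bleeding that is m/12 on-drug for m months of prior use, and wholly on-drug from 12 months, for a period that the listed bleed history does not cover. The comparator in 9.1.2 shrinks to 12 − m months and is empty from 12 months.

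How much this moves any result is unknown. The 5.0, 8.0 and 4.0 above are illustrations that rest on an assumed pre-drug ABR of 6 to 12. The overall primary ABR estimate is not affected; the breakdown by bleeding profile and one secondary endpoint are. This is an inconsistency worth correcting because correction is cheap, not a flaw that threatens the study's main result.

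**What to change.** In sections 9.1.2 and 9.7.1, replace the enrollment anchor by the start of damoctocog alfa pegol therapy. Both then agree with 9.1, 9.3.2, 9.3.4, 9.7.2 and 9.7.4. For naive patients this changes almost nothing. Use that one pre-drug variable for the bleeding-profile strata and for the before/after comparison, and report the comparison separately for naive and non-naive patients.

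The cost is two phrases. The bleed history is already collected on this window, and 9.3.7 records the date on which damoctocog was started, so no new data or visits are needed. The drawback is that long-standing users must recall, or have records for, an older period, and 9.3.2 says prior bleeds are estimated by patient and physician. Reporting naive and non-naive patients separately keeps that weakness visible.

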### **Missing data:**

Because the aim of this study is to obtain data under conditions of routine clinical care (i.e., naturalistic settings), some patients may have missing values for some variables. To address missing data, the following strategy will be applied:

- In general, clinical outcomes collected in the study will not be imputed.
- Impute missing exposure and AE/concomitant medication start and/or end date based on a “worst case” scenario.
- In cases when imputation is necessary, reasons for missing data will be identified (such as: due to loss to follow-up, skip question patterns in the eCRF, or random data collection issues) and appropriate methods of analysis (such as last-observation-carried-forward, impute to the mean, maximum likelihood, and multiple imputation) will be selected based on reasonable assumptions.

The SAP will describe in detail the methods and variables used in the analyses, including those pertaining to truncated and missing data. Furthermore, the extent of missing or truncated data within the analysis datasets will be described in clinical study reports.

### **Exposure risk-window for safety analysis:**

Patients may switch damoctocog alfa pegol treatment regimen and/or may permanently discontinue from damoctocog alfa pegol treatment during the study. In general, only the patient time during which patients are receiving treatment with prophylactic damoctocog alfa pegol will be included in person-years denominator when estimating rates of safety outcomes for prophylactic damoctocog alfa pegol.

### **Confounders and effect-modifying factors:**

Because of the non-interventional character of the study, results may be subject to bias and confounding. Multiple regression and stratified analysis will be used in this study to control for differences between groups.

Influencing factors such as treatment regimen, severity of hemophilia, patient bleeding profiles, sex, time on treatment, and age groups will be used as the basis for defining sub-populations for the main analysis.

Covariates included in the study are those determined to be risk factors for a given outcome of interest or predictors of exposure, such as medical histories, pre-treatment history, and country. Covariates will be determined at baseline and be used for regression model development. Detailed methodologies and analysis process will be documented in the SAP.

### **9.7.2 Analysis of demography, disease details, prior and concomitant medication/treatment, and other baseline data**

Demographics and baseline disease characteristics will be described by frequency tables or summary statistics. Baseline disease characteristics will include the most recent FVIII product used prior to the start of damoctocog alfa pegol treatment. Some continuous variables will be categorized and presented in frequency tables in addition to summary statistics. Categories will be defined in the SAP.

Number of bleeds prior to enrollment (or first administration of the study drug, for damoctocog alfa pegol non-naïve patients) into the study will be summarized.

Prior and concomitant medication/treatment and medical history will be presented by frequency tables or summary statistics.

### **9.7.3 Analysis of treatment exposure**

Analysis of treatment exposure will be performed on the SAF.

In this study, the following 4 types of exposure based on physician's prescription will be considered:

- Prophylaxis: twice weekly (including any prescription more than 7 times per month).
- Prophylaxis: every 5 days (including any prescription between >5-7 times per month).
- Other: if not listed above.
- All.

The damoctocog alfa pegol exposure will start with the first infusion in the study. The period of continuous exposure per treatment pattern (following approved local label), stops whenever prescribed damoctocog alfa pegol treatment regimen changes. Treatment patterns for non-naïve patients will also be summarized.

Exposure duration (in days) will be analyzed descriptively by summary statistics and frequency tables per treatment pattern.

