### **7.3 Background**

Prophylaxis with FVIII reduces bleeds and improves joint outcomes in patients with severe hemophilia A [11],[12],[13],[14], and it is therefore the standard of care in most developed countries [2],[15]. However, adherence to prophylaxis is poor in some patients [16]. This may be due to the high time burden and inconvenience of a typical prophylaxis regimen, which requires intravenous infusion at least 2 or 3 times per week [17],[18],[19]. Thus, prolonged-half-life FVIII products that allow for less frequent, individualized dosing may increase adherence and ultimately lead to improved clinical outcomes, including prevention of joint disease [20],[21],[22].

In a phase I study of 14 patients, damoctocog alfa pegol had a half-life of ~19 hours versus ~13 hours for sucrose-formulated rFVIII [8]. In the phase II/III PROTECT VIII study [9], median annualized bleeding rate (ABR) was 2.1 for patients using damoctocog alfa pegol twice weekly, every 5 days, and every 7 days [9], and 1.5 during the long-term extension study. Safety was comparable to that observed with other FVIII products [23],[24],[25],[26],[27]. Patients and physicians can choose from 3 effective prophylaxis regimens with damoctocog alfa pegol based on individual patient bleeding profile and lifestyle. However, there are currently no data regarding real-world use of the product outside of the clinical study.

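### The exposure classes in Section 9.7.3 have no every-7-days prophylaxis class, so the regimen-stratified ABR gives no separate estimate for one of the three regimens named in Section 7.3

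*Protocol*

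**What the plan says.** Protocol Section 7.3 (Background) describes the earlier phase II/III results for "damoctocog alfa pegol twice weekly, every 5 days, and every 7 days" and adds: "Patients and physicians can choose from 3 effective prophylaxis regimens with damoctocog alfa pegol".

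Section 8.1 makes the primary objective an analysis of ABR in the different prophylaxis regimens, whether on the local label or otherwise prescribed in normal practice. It does not list the regimens.

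Section 9.7.1 (Sub-populations) says: "Data will be stratified by prophylaxis dosing regimen (following approved local label, see Section 9.7.3". Section 9.7.3 then states that "the following 4 types of exposure based on physician's prescription will be considered". They are:

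- first, a twice-weekly prophylaxis class, which takes every prescription above 7 per month;
- second, "Prophylaxis: every 5 days (including any prescription between >5-7 times per month";
- third, a residual class, worded "Other: if not listed above";
- fourth, all patients.

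Four types are announced and four are listed, so no line has been lost.

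Sections 9.1 and 9.2.1 admit on-demand, prophylaxis and intermittent-prophylaxis patients. Section 9.7.4 restricts the primary ABR analysis to patients on prophylactic treatment, in the FAS. It allows analysis within the Section 9.7.1 subgroups if needed and if the data permit.

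**The concern.** The protocol presents three prophylaxis regimens but provides prophylaxis classes for two. Because the regimen strata are tied by cross-reference to the Section 9.7.3 list, the third regimen disappears into a residual class.

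Two things are at stake. First, a reader who wants the ABR by regimen, which is how the primary objective is framed, gets no figure for every-7-days prophylaxis. Second, the residual class is the only individual class not labelled as prophylaxis. In the exposure analysis on the SAF it takes every-7-days prophylaxis, on-demand treatment, and any intermittent or other prophylaxis that meets neither frequency bound. A summary of that class describes no recognisable way of using the product.

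This is not detail left to the SAP. Section 9.7.1 leaves to the SAP the assignment of patients after a regimen change or a switch to on-demand, and the choice of further subgroups. The base classes are fixed in the protocol itself.

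**Working it through.** **1. Which class does each regimen fall into?**

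Inputs: the bounds >7 and >5 to 7 per month (Section 9.7.3) and the three regimens (Section 7.3). The protocol does not say how long a month is, so I use 28, 30, 30.44 and 31 days.

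Formula: infusions per month = days in month / dosing interval in days.

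| Regimen | 28 d | 30 d | 30.44 d | 31 d | Class |
|---|---|---|---|---|---|
| Twice weekly (3.5 d) | 8.00 | 8.57 | 8.70 | 8.86 | >7 |
| Every 5 days | 5.60 | 6.00 | 6.09 | 6.20 | >5 to 7 |
| Every 7 days | 4.00 | 4.29 | 4.35 | 4.43 | *Other* |

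The first two regimens land where intended. Every 7 days never exceeds 5 per month, so it is in *Other* whatever month length is used.

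Intermediate schedules depend on the month length. Every 6 days is 4.67, 5.00, 5.07 or 5.17, on either side of the >5 bound. Every 4 days is 7.00, 7.50, 7.61 or 7.75, on either side of the >7 bound.

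**2. What precision would a separate class have?**

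The protocol's own figures come first. Section 9.5 takes ABR as negative binomial with μ = 6 and θ = 1. The log-scale 95% interval is μ·exp(±1.96·s), with s = √[(1/μ + 1/θ)/n], so the half width is μ·[exp(1.96·s) − exp(−1.96·s)]/2.

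For n = 36: s = √(1.1667/36) = 0.180 and 1.96·s = 0.353, so the half width is 6 × (1.423 − 0.703)/2 = 2.16.

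| n | Computed | Table 4 |
|---|---|---|
| 36 | 2.16 | 2.17 |
| 108 | 1.23 | 1.23 |
| 180 | 0.95 | 0.96 |

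The half widths reproduce. This does not check the probability statement that Section 9.5 attaches to the last one.

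The protocol gives no share of patients on every 7 days, so I assume a range, applied to the 180 evaluable patients (200 × 0.90):

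| Assumed share | n | Half width |
|---|---|---|
| 10% | 18 | 3.12 |
| 20% | 36 | 2.16 |
| 30% | 54 | 1.75 |
| 40% | 72 | 1.51 |

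At 20% the class is the first row of Table 4, a subgroup size the protocol already contemplates. Splitting the residual class changes neither the total of 180 nor the overall half width of 0.96.

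**The case against.** The strongest defence is that Section 9.7.3 is about exposure on the SAF, while the primary ABR population is set separately in Section 9.7.4 as patients on prophylactic treatment, with their prophylactic period as the offset. That stands. A reader might infer that the scheme forces a choice between dropping every-7-days patients from the primary analysis and letting on-demand patients in. The protocol does not support this: nowhere does it define prophylaxis as everything outside *Other*, and it recognises modality independently of the four classes. Within the primary analysis, *Other* would mix every-7-days with other infrequent or intermittent prophylaxis, not with on-demand treatment.

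The three regimens are named in the background, beside earlier trial results, and not in the objective. The objective refers to local labels, which are not in the protocol. This too is fair, but Section 8.1 also covers any other regimen the physician prescribes, so every-7-days use is in scope whatever a label says.

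The stratified analyses are conditional, the prescribed regimen is recorded (Section 9.3.7), and the SAP may add subgroups. So the stratum can be recovered, and it would be too strong to say that the primary objective cannot be met. But recovery would mean departing from the classes the protocol fixes, which is better done before bleeding data are analysed.

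A reader might also infer that the shift table cannot tell a move to once weekly from a move to on-demand. Section 9.7.5 bases that table on the prescribed regimen and does not cite the four classes, so this follows only if those classes are used there.

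**Conclusion.** The inconsistency between Sections 7.3, 9.7.1 and 9.7.3 is real and does not depend on the month length used. As written, one of three named prophylaxis regimens gets no separate ABR, and the residual exposure class does not distinguish prophylaxis from on-demand treatment.

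The effect is limited to regimen-level reporting. The primary endpoint in Section 9.1.1 has no regimen split, and the overall prophylaxis ABR can be estimated as planned. No number of patients lost from the primary analysis, and no size for a mixed ABR, can be supported: the protocol gives neither the share of patients on each regimen nor an ABR for on-demand treatment. The precision figures for a separate class rest on an assumed share of 10% to 40%.

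This should be fixed, ideally before the SAP is finalised. It does not undermine the study.

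**What to change.** Reconcile Sections 7.3, 9.7.1 and 9.7.3. The change concerns analysis classes only, not how patients are treated.

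- Add a class for every-7-days prophylaxis with a stated frequency range. Its upper bound should be 5 per month, so that it meets the existing >5 bound without a gap. Its lower bound should be no higher than 4.0, so that the regimen stays in on a 28-day month.
- Split the remainder into prophylaxis at other frequencies, intermittent prophylaxis, and on-demand. Keep the last two apart: intermittent prophylaxis is preventive, and merging it with on-demand would recreate the mixture.
- Assign modality first and frequency second, so that the classes do not overlap, and state the month length used for conversion.
- State in Section 9.7.4 which classes form the prophylaxis population for the primary ABR analysis.
- Use the same classes in Section 9.7.5.

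The cost is text and a few extra table columns, some with small n. No new data are needed, assuming that the prescribed-regimen field in Section 9.3.7 identifies on-demand and intermittent use (the CRF is not shown). Total sample size and overall precision do not change.
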